## Summary Table of Study Protocol

Title	Post-marketing Study Evaluating the Risk of Serious Cardiovascular Events Among Osteoporotic Patients Receiving Romosozumab in Japan Using the Medical Information Database Network (MID-NET)
Protocol version identifier	Study Number 20190206; Version 1.0
Date of last version of the protocol	04 April 2024
EU Post Authorization Study (PAS) Register No	To be determined
Active Substance	Romosozumab
Medicinal Product	Evenity®
Device	NA
Product Reference	NA
Procedure Number	NA
Joint PASS	No
Research Question and Objectives	Primary objective To evaluate the risk of serious cardiovascular events during the initial 12 months of romosozumab therapy relative to other specific osteoporosis therapies Secondary objective To evaluate the risk of serious cardiovascular events during the initial 12 months of romosozumab therapy relative to other specific osteoporosis therapies by the level of renal insufficiency
Country(ies) of Study	Japan
Author	PPD

## Study Design Schema

 Censor at index drug discontinuation (including medication switch), one-year after index date, end of available data in the database, or death.

MID-NET	Outpatient Dx, Px, Rx, Labs	Observable Data
Outside MID-NET	Outpatient Dx, Px, Rx, Labs	Incomplete Observability
MID-NET	Inpatient Dx, Px, Rx, Labs	Observable Data
Outside MID-NET	Inpatient Dx, Px, Rx, Labs	Incomplete Observability
In-hospital death		Observable Data

Abbreviations used in the figure: CV, cardiovascular; PTH, parathyroid hormone receptor.

## 2. List of Abbreviations

Abbreviation or Special Term	Explanation
CCI	CCI
CCI	CCI
BMD	Bone mineral density
BRIDGE	Study to Compare the Safety and Efficacy of Romosozumab versus Placebo in Men with Osteoporosis
CI	Confidence intervals
CKD	Chronic kidney disease
CCI	CCI
EMR	Electronic medical records
FRAME	Fracture Study in Postmenopausal Women with Osteoporosis
GPSP	Good post-marketing study practice
ICMJE	International Committee of Medical Journal Editors
IPTW	Inverse probability of treatment weights
IQR	Interquartile range
J-RMP	Japanese Risk Management Plan
MDV	Medical Data Vision
MHLW	Ministry of Health, Labor, and Welfare
MID-NET	Medical Information Database Network
NDB	National database
PMDA	Pharmaceuticals and Medical Devices Agency
PPV	Positive predictive value
PTH	Parathyroid hormone receptor
SAP	Statistical analysis plan
SD	Standard deviation
SERM	Selective estrogen receptor modulators
SMD	Standardized mean differences
SMRW	Standardization mortality rate weighting

#### 4. Abstract

- Study Title

Post-marketing Study Evaluating the Risk of Serious Cardiovascular Events Among Osteoporotic Patients Receiving Romosozumab in Japan Using the Medical Information Database Network (MID-NET).

- Study Background and Rationale

In January 2019, romosozumab was approved in Japan for the treatment of osteoporosis in patients at high risk of fracture. As part of the Japanese Risk Management Plan for romosozumab, Amgen committed to conduct a post-marketing study to evaluate the risk of cardiovascular events in real-world users of romosozumab and those with renal dysfunction. The overall approach of the proposed study, including study design, the data source, endpoints, comparator group, and overall analytic approach was previously agreed upon with the agency during the consultation meeting held on January 17, 2024.

- Study Feasibility and Futility Considerations

Sample size in MID-NET has been informed by publicly available data. The confidence interval around the effect estimate is expected to have low precision due to low event rate. We followed the draft ICH M14 guidance “General Principles on Planning and Designing Pharmacoepidemiological Studies That Utilize Real-World Data for Safety Assessment of a Medicine” to interpret the study results. Questions around the measured and unmeasured confounders, potential channeling bias, definition of baseline period, and level of renal insufficiency are addressed by National database (NDB) open data and Amgen in-house using the database provided by Medical Data Vision (MDV).

- Research Question and Objectives

The phase 3 randomized controlled trial (ARCH) showed more cardiovascular death, nonfatal MI, and nonfatal CCI in patients treated with romosozumab than in those treated with alendronate. However, this trial did not include any Japanese women. Therefore, the objective of this study is to assess the cardiovascular safety of romosozumab in Japanese patients.

Objectives	Endpoints
Primary	

To evaluate the risk of serious cardiovascular events during the initial 12 months of romosozumab therapy relative to other specific osteoporosis therapies

	

Composite endpoint of hospitalized acute myocardial infarction, cerebral hemorrhage and cerebral infarction

Secondary	


To evaluate the risk of serious cardiovascular events during the initial 12 months of romosozumab therapy relative to other specific osteoporosis therapies by the level of renal insufficiency

	

Composite endpoint of hospitalized acute myocardial infarction, cerebral hemorrhage and cerebral infarction

- CCI [REDACTED]
  - CCI [REDACTED]
  - CCI [REDACTED]
  - CCI [REDACTED]
  - CCI [REDACTED]
- Estimation
  - This study will estimate the hazard ratio (95% confidence interval) of hospitalized cardiovascular events for romosozumab relative to other specific osteoporosis therapies. Interpretation of the estimate will be informed by available sample size, completeness of capture for the endpoints, and the assessment of measured and unmeasured confounding.
- Study Design

A retrospective cohort study of a new user with active comparator design
- Data Resource

MID-NET database is a hospital-based setting of 23 hospitals from ten healthcare organizations that participate in the CCI [REDACTED] system. The patient-level data includes clinical, administrative and laboratory information. Previous studies showed the high validity of the diagnoses and procedure records in the CCI [REDACTED] database, which are used to enhance healthcare service management for health policy planning. In 2022, nearly 1.5 million patients had a record in this network.

- Patient Eligibility Criteria

Inclusion criteria

- Three cohorts of patients defined by new initiation of romosozumab, Parathyroid hormone receptor (PTH) analogs (teriparatide, abaloparatide) or oral alendronate from 4 March 2019 onwards to one year prior to the end of available data.
- Patients at least 50 years of age at the date of new treatment initiation.

Exclusion criteria

- Patient without an adequate period of records in the data source for assessment of baseline cardiovascular risk.

[figure not shown]
- Follow-up

Patients will be followed from the initiation of romosozumab, PTH analogs or oral alendronate (index date) through the first occurrence of any of following: endpoint, discontinuation of the study medication (including medication switch), one year after index date, end of available data in the database, or death.

- Variables

- Outcome Variables

Two types of outcomes will be defined using algorithms that have been previously validated in Japan administrative claims databases.

- Exposure Variables

Three cohorts will be created mutually and defined based on the prescriptions received for:

- Romosozumab
- PTH analogs: teriparatide, abaloparatide
- Oral alendronate

- Covariates

- Patient and healthcare characteristic
- Fracture risk factors
- Cardiovascular risk factors
- Use of cardioprotective therapies
- Historical use of anti-osteoporosis drugs
- Level of renal insufficiency

- Study Sample Size

Using the MID-NET 2021 open data, we estimated the number of patients who received romosozumab, teriparatide, or oral alendronate over 5.5 years. The expected sample size for this study is: 3,850 patients for romosozumab, 8,500 patients for teriparatide, and 60,000 patients for oral alendronate.

- Data Analysis

- Summary Statistics:

Patient demographic and clinical characteristics will be summarized by cohort of exposure. Discrete variables will be summarized using frequencies and proportions, and continuous variables will be summarized using means and standard deviation (SD) or median and interquartile range (IQR). Incidence rate (number of events divided by person-time of follow-up) of the various outcomes in each exposure cohort will be estimated along with 95% confidence intervals (CI) as a measure of precision.

- Approach to primary objective:

Propensity scores will be calculated for each patient using multiple logistic regression modelling based on baseline demographic characteristics and clinical characteristics. Inverse probability of treatment weights (IPTW) will be created using propensity scores to minimize the measured confounding in the comparison of patients initiating romosozumab relative to patients initiating other specific osteoporosis therapies. Standardized mean differences (SMD) will be used to assess the differences in baseline patient characteristics between the treatment groups. Negative control outcome analyses will be used to detect presence of unmeasured confounding. COX proportional hazards model in the weighted sample will be used to estimate hazard ratio.

- Approach to secondary objective:

The same approach will be performed by the level of renal insufficiency:

1) no chronic renal disease (or eGFR  $\geq 90$  mL/min/1.73 m^2), 2) stage I or II Chronic Kidney Disease (CKD) (or eGFR 60-89 mL/min/1.73 m^2), 3) stage III CKD (or eGFR 30-59 mL/min/1.73 m^2), or 4) stage IV or V (or eGFR  $< 30$  mL/min/1.73 m^2).

- Bias analysis:

To inform the reliability and robustness of interpreting the results, we plan to perform a series of bias analyses that may include:

- Evaluate completeness of follow-up capture of outcomes in MID-NET (an open healthcare system) relative to a closed healthcare system (for example, DeSC, NDB) within therapy cohort
- Quantitative bias analysis to characterize the magnitude of uncertainty arising from systematic errors

## 5. Amendments and Updates

Amendment or Update Number	Date	Section of Study Protocol	Amendment or Update	Reason
1.0	27 June 2024	NA	NA	The initial version.

## 6. Rationale and Background

### 6.1 Summary of the Medicinal Product of Interest

**Table 1. Summary of the Medicinal Product of Interest**

Date of Approval	08 January 2019
Date of Market Launch	04 March 2019
Therapeutic Classification	CCI
Re-examination Period	8 years
Approval Number	CCI
Brand Name	Evenity® Subcutaneous Injection 105 mg Syringes
Active Substance	Romosozumab
Dose and Formulary	Injection: Containing 105 mg of romosozumab in a prefilled syringe (1.17 mL).
Administration Route and Dosage	Adult: 210 mg of romosozumab once monthly for 12 months.
Indication	Osteoporosis in patients at high risk of fracture.
Conditions for Approval	The risk management plan should be developed and implemented as appropriate.

### 6.2 Safety Specification

This study investigates 1) serious cardiovascular events listed as an important potential risk and 2) safety in the patients with renal dysfunction as important missing information. This study is a part of additional pharmacovigilance activities described in the Japanese Risk Management Plan (J-RMP) for romosozumab (Evenity®).

### 6.3 Diseases and Therapeutic Area

Osteoporosis is a disease characterized by low bone mineral density (BMD), deterioration of bone tissue, and disrupted bone microarchitecture resulting in compromised bone strength and risk of fractures (Amgen, 2019a; LeBoff et al, 2022). Osteoporosis can be prevented and treated with lifestyle modification, medication and supplements (The Committee for Developing Guidelines for Prevention and Treatment of Osteoporosis, 2015). Pharmacologic therapeutics for anti-osteoporosis focus on reducing bone loss (using antiresorptive agents) and increasing bone formation (using anabolic agents). These approaches aim to improve bone density and strength. Antiresorptive agents, such as bisphosphonate, RANKL antibody (denosumab), estrogen replacement therapy, or selective estrogen receptor modulators (SERMs),

along with anabolic agents like PTH analogs, have demonstrated efficacy in clinical trials for reducing fracture. Additionally, supplement treatment like calcium, activated vitamin D3, and vitamin K derivatives can be beneficial. Furthermore, calcitonin salmon is used to alleviate osteoporosis-related pain (LeBoff et al, 2022; Sözen et al, 2017).

In January 2019, romosozumab was approved in Japan for the treatment of osteoporosis in patients at high risk of fracture. Romosozumab is a monoclonal antibody that binds and inhibits sclerostin, a natural inhibitor of the Wnt signaling pathway, therefore increasing bone formation and decreasing bone resorption.(Cosman et al, 2016; Lim, 2022). Two phase III, international, randomized, double-blind, placebo-controlled trials of romosozumab were evaluated for the approval in Japan: The Fracture Study in Postmenopausal Women with Osteoporosis (FRAME) (Cosman et al, 2016) and a study to compare the safety and efficacy of romosozumab versus placebo in men with osteoporosis (BRIDGE) (Lewiecki et al, 2018). Results from the FRAME trial showed risk reductions for new vertebral fractures and clinical fractures at 12 and 24 months as well as the increases in BMD at the lumbar spine, total hip, and femoral neck among patients treated with romosozumab compared to placebo (Cosman et al, 2016). Results from the BRIDGE trial demonstrated increased BMD in the romosozumab group, compared to placebo group (Lewiecki et al, 2018).

Romosozumab may potentially cause or worsen vascular calcification, but pre-clinical data indicate no impact on cardiovascular events (Amgen, 2019b). However, in an international, randomized trial of postmenopausal women with osteoporosis at high risk of fracture, romosozumab was associated with more serious cardiovascular events (2.5% versus 1.9%) than alendronate in the first 12 months (Saag et al, 2017). This trial did not include Japanese patients, unlike the FRAME study, which showed no difference (1.3% versus 1.3%) between the two treatments (Amgen, 2019b; Cosman et al, 2016). In September 2019, the Japanese package insert for romosozumab was updated in response to adverse drug reports following its launch. The revision included safety precautions related to cardiovascular events, as advised by Ministry of Health, Labor, and Welfare (MHLW) and Pharmaceuticals and Medical Devices Agency (PMDA) (PMDA, 2019).

#### **6.4 Rationale**

As part of the Japanese Risk Management Plan for romosozumab, Amgen committed to conduct a post-marketing study to evaluate the risk of cardiovascular events in real-world users of romosozumab and those with renal dysfunction. As renal dysfunction is

associated with higher risk of cardiovascular events (Jankowski et al, 2021) and vascular calcification, especially in people on dialysis (Amgen, 2019b), this study will examine the risk of the cardiovascular events by the level of renal insufficiency. The overall approach of the proposed study, including study design, the data source, endpoints, comparator group, and overall analytic approach was previously agreed upon with the agency during the consultation meeting held on January 17, 2024.

### **6.5 Feasibility and Futility Considerations**

We used publicly available data to determine the sample size in MID-NET. The effect estimate's confidence interval may have low precision because of the low event rate. We used the NDB open data to describe the challenge of measured and unmeasured confounders in this study, and followed the draft ICH M14 guidance "General Principles on Planning and Designing Pharmacoepidemiological Studies That Utilize Real-World Data for Safety Assessment of a Medicine" to perform bias analysis for study results interpretation. Given that MID-NET operates within a hospital-based setting and is currently inaccessible, we conducted feasibility assessments using Medical Data Vision (MDV) data to inform the choice of baseline period and the renal impairment level for protocol development. Amgen CfOR Data Analytics Center performed the internal analysis of MDV. The results suggest that sample size may not significantly increase even with a 3-month baseline period. In line with PMDA's recommendation, a 12-month period is set as the baseline for this study. In addition, the diagnosis of CKD stages did not have enough sensitivity to describe the level of renal impairment in the MDV data. Instead, using serum creatinine and estimated glomerular filtration rate (eGFR) can provide a more accurate and granular classification of renal insufficiency among osteoporosis patients. The MID-NET summary report I stated that more than 90% of patients who were given romosozumab (1908 out of 1989), alendronate (18,570 out of 19,118) or PTH analogs (2,978 out of 3,156) had their serum creatinine tested during 2021-2023 (PMDA, 2024a).

### **6.6 Statistical Inference (Estimation)**

This study will estimate the hazard ratio with 95% confidence interval of cardiovascular events for romosozumab relative to other specific osteoporosis therapies. Interpretation of the estimate will be informed by available sample size, completeness of capture for the endpoints, and the assessment of measured and unmeasured confounding.

## 7. Research Question and Objectives

The phase 3 randomized controlled trial (ARCH) showed more cardiovascular death, nonfatal MI, and nonfatal CCI in patients treated with romosozumab than in those treated with alendronate. However, this trial did not include any Japanese women. Therefore, the objective of this study is to assess the cardiovascular safety of romosozumab in Japanese patients when compared to other anti-osteoporosis medications.

### 7.1 Primary

The objective of this study as follows:

To evaluate the risk of serious cardiovascular events during the initial 12 months of romosozumab therapy relative to other specific osteoporosis therapies.

romosozumab vs. PTH analogs  
romosozumab vs. oral alendronate

### 7.2 Secondary

To evaluate the risk of serious cardiovascular events during the initial 12 months of romosozumab therapy relative to other specific osteoporosis therapies by the level of renal insufficiency

romosozumab vs. PTH analogs  
romosozumab vs. oral alendronate

## 8. Research Methods

### 8.1 Study Design

This is a retrospective cohort study employing a new user with active comparator design, using secondary data and conducting analyses in MID-NET database.

### 8.2 Setting and Study Population

#### 8.2.1 Study Period

Patients will be identified for inclusion into the study population between 04 March 2019 (initial date of use for specific coding for romosozumab, PTH analogs (teriparatide, abaloparatide) or oral alendronate) through and the date of data extraction. Data availability will extend to 365 days prior to index date to accommodate the identification of eligible patients. Patients will be eligible to enter the cohort up to one year prior to the end of available data, ensuring a potential minimum follow-up period of one year.

## **8.2.2 Subject Eligibility**

### **8.2.2.1 Inclusion Criteria**

Three cohorts of patients defined by new initiation of romosozumab, PTH analogs (teriparatide, abaloparatide) or oral alendronate from 4 March 2019 onwards to one year prior to the end of available data.

Patients at least 50 years of age at date of new treatment initiation.

### **8.2.2.2 Exclusion Criteria**

Patients without at least 365 days before new treatment initiation.

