## **8.2.4 Baseline Period**

The baseline period will be identified as 365 days before the index date (exclusion the index date). For three cohorts of patients with study medication (romosozumab, PTH analogs (teriparatide, abaloparatide) or oral alendronate), we will use all historical data prior to index date (exclusive) to identify new use of the index drug.

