## **8.2.5 Study Follow-up**

Patients will be followed from the initiation of romosozumab, PTH analogs or oral alendronate (index date) through the first occurrence of any of following: endpoint, discontinuation of the study medication (including medication switch), one year after index date, end of available data in the database, or death.

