### 8.3.2 Outcome Assessment

Outcome of primary objective and secondary objective:

Cardiovascular end points will be defined using algorithms that have been previously validated in Japan administrative claims databases and recommended by agency (Ando et al, 2018; Nakai et al, 2021; PMDA, 2023a; PMDA, 2023b; PMDA, 2023c).

Endpoint will be the first admission date for each outcome, and the event will be identified with a diagnosis related to primary, admission-causing or most-resourcing categories.

We will use the admission date as the event date to capture the earliest sign of the event. We recognize that the admission date may not represent the actual onset of event if it occurs during hospitalization. However, we expect that this effect is likely small in general, since the average hospital stay related to cardiovascular events was reported to be approximately 15 days (JCS, 2023). Moreover, the subgroup of the patients using index medication (ie, romosozumab, teriparatide, or oral alendronate) during hospitalization is less than 10% (MHLW, 2023a). Therefore, the use of admission date as the date of event occurrence is appropriate for this study.

CCI

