### **8.3.3 Covariate Assessment**

Covariates that might influence osteoporosis treatment choice (ie, measures of prognosis) and are risk factors for various adverse events that could be assessed in safety evaluation are included to control for confounding. Sex, age and year of index date will be included as a covariate. All available historical data will be used to assess

history of fracture, history of pharmacologic therapy for osteoporosis, history for cardiovascular risk factor, history of cardioprotective therapies and or osteoporosis-related medication. Each covariate will be identified using a case ascertainment algorithm that incorporates individual or combinations of inpatient and outpatient ICD-10 diagnosis codes, drug codes, procedure codes, laboratory test codes, and date information from the MID-NET system. Covariates with a prevalence of 0.5% or less in the feasibility assessment within MID-NET will not be included in this study.

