Corticosteroids (oral or injectable)	Yes	
Opioids	Yes	
Proton-pump inhibitor	Yes	
History of other comorbidities that increased fracture or osteoporosis risk		Fracture/OP risk factors. Within one year prior to index
Rheumatoid arthritis	Yes	
Systemic Lupus Erythematosus	Yes	
Chronic obstructive pulmonary disease	Yes	
Asthma	Yes	
Pneumonia	Yes	
Parkinsonism	Yes	
Dementia	Yes	
Depression	Yes	
Schizophrenia	Yes	
Sepsis or septicemia	Yes	
Sleep apnea	Yes	
Vitamin D deficiency	Yes	
History of cardiovascular events		All available history unless otherwise specified
Myocardial infarction within 1 year prior to index	Yes	Within one year prior to index
Myocardial infarction $\geq$ 1 year prior to index	Yes	$\geq$ 1 year prior to index
CCI within 1 year prior to index	Yes	Within one year prior to index
CCI $\geq$ 1 year prior to index	Yes	$\geq$ 1 year prior to index
History of CV risk factors		Within one year prior to index
Atherothrombosis	Yes	
Heart failure	Yes	
Peripheral artery disease	Yes	

Characteristic	MID-NET	Note/ Covariate assessment period
Cerebrovascular disease	Yes	
Coronary artery disease	Yes	
Angina (including stable and unstable)	Yes	
Atrial fibrillation	Yes	
Conduction disorder	Yes	
Hypertension	Yes	
Hyperlipidemia	Yes	
Hypercholesterolemia	Yes	
Obesity	Yes	
Peripheral vascular disease	Yes	
Transient ischemic attack	Yes	
Type 2 diabetes mellitus	Yes	
CKD	Yes	
Chronic kidney disease (stage III, IV and V) without dialysis	Yes	
Chronic kidney disease (stage III, IV and V) with dialysis	Yes	
End stage renal disease	Yes	
History of cardioprotective therapies		Within one year prior to index
Diuretic		Antihypertensive
Beta-blocker		Antihypertensive
Calcium Channel blockers		Antihypertensive
Angiotensin Converting Emzyme (ACEI)/ Angiotensin Receptor Blockers (ARBs)	Yes	Antihypertensive
Insulin	Yes	Anti-diabetes
Metformin	Yes	Anti-diabetes
GLP-1 receptor agonists	Yes	Anti-diabetes
Thiazolidinediones	Yes	Anti-diabetes
Sulfonylureas	Yes	Anti-diabetes
SGLT- 2 inhibitors	Yes	Anti-diabetes
DPP- 4 inhibitors	Yes	Anti-diabetes
Statins (any kind)	Yes	lipid lower agents
Ezetimide	Yes	lipid lower agents
Statins + ezetimide combinations	Yes	lipid lower agents
PCSK9i	Yes	lipid lower agents
Other lipid lowering drugs (fibrates, gemfibrozil, Niacin, Cholestyramine)	Yes	lipid lower agents
Aspirin	Yes	Antiplatelets/ antithrombotic
Clopidogrel and other antiplatelet	Yes	Antiplatelets/ antithrombotic

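### As written, an MI or stroke admission on the index date counts as an on-drug event, and the 0.5% prevalence filter could remove recent MI or stroke from the propensity model

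*Protocol*

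**What the plan says.** - **Eligibility.** Apart from age and new use, the only bar to entry in Section 8.2.2.2 is short history: "Patients without at least 365 days before new treatment initiation". No event-free interval is required. Table 3 lists "Myocardial infarction within 1 year prior to index" as a covariate, and beside it a second recent-event item whose name is blacked out. Patients with a recent event are therefore admitted by design and handled by adjustment.
- **Baseline.** Section 8.2.4: "The baseline period will be identified as 365 days before the index date (exclusion the index date". Table 3 includes the index date itself for laboratory and lifestyle values, but does not say so for cardiovascular history.
- **Follow-up.** Section 8.2.5: "Patients will be followed from the initiation of romosozumab, PTH analogs or oral alendronate (index date) through the first occurrence" of the listed end points. No lag is stated.
- **Endpoint.** Section 8.3.2: "Endpoint will be the first admission date for each outcome", identified from a leading diagnosis field and dated at admission. The visible text has no rule for transfers, same-episode readmissions or index-day admissions. Table 2, which holds the algorithms, is redacted.
- **Covariate filter.** Section 8.3.3: "Covariates with a prevalence of 0.5% or less in the feasibility assessment within MID-NET will not be included in this study".
- **Labelling.** Section 6.3 says of the Japanese package insert for romosozumab: "The revision included safety precautions related to cardiovascular events". Section 8.7.2.5.4 also refers to precautionary use of romosozumab.

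**The concern.** Day 0 belongs to follow-up and not to baseline. A patient admitted with a stroke who is first prescribed the study drug on that date has an event at time zero that the drug can hardly have caused, and the same admission is not recorded as history.

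A patient whose MI came days before index can also be readmitted or transferred for the same episode. Unless the redacted algorithm prevents it, that admission looks like a new event.

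The main defence is propensity weighting on recent events, but the filter may delete those covariates. Even if they stay, a one-year window does not separate an event 5 days before index from one 350 days before, and weighting does not correct a misclassified outcome.

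Two directions of bias are possible. If these events fall more in the comparators, the hazard ratio is pulled down. If they are equally frequent in all cohorts, a hazard ratio other than 1 is pulled toward 1. In a study commissioned to look for cardiovascular harm, either could hide a signal.

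**Working it through.** **Inputs from Section 8.5.** 3,850 romosozumab, 8,500 PTH-analog and 60,000 alendronate patients; event rates of 0.004 or 0.01 per person-year; follow-up of 0.6 or 0.8 years (midpoint 0.7 used below).

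**Assumptions not in the protocol.** Prior-year event prevalence equals the planning rate times one year. Events are spread evenly over that year. Same-episode readmission is 5% to 20%, and is possible only after an event in the last 30 or 90 days.

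**1. Reproduce Table 4.** SE(log HR) = sqrt(1/e1 + 1/e0), where e = N × rate × follow-up. At 0.004 and 0.6 years, e1 = 9.24, and e0 = 20.4 (PTH) or 144 (alendronate). The intervals are 0.46 to 2.18 and 0.51 to 1.95, against 0.45 to 2.18 and 0.50 to 1.91 stated. Across all eight cells the SE agrees within about 2%. Table 4 is sound, and these event counts can be used.

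**2. Day 0.** Section 8.2.4 ends baseline on day −1. Section 8.2.5 opens follow-up on day 0. Section 8.3.2 dates the event at admission. Together they make an index-day admission an outcome. The protocol gives no count of such admissions. Purely as a scale, if 0.1% of PTH patients had one, that would be 8.5 events, or 42% of the 20.4 expected at the lowest planning rate and follow-up.

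**3. The filter.** 0.004 × 1 year = 0.4%, below the 0.5% cut even for the whole composite. 0.01 × 1 year = 1.0%, above the cut for the composite. Table 3 lists MI separately, however, so its own prevalence is lower than either figure.

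**4. Same-episode readmissions, alendronate.** Prior-year events: 60,000 × 0.004 = 240, or × 0.01 = 600. True follow-up events: 60,000 × 0.7 × 0.004 = 168, or × 0.01 = 420. Let f = false/true = (w/365 × r)/0.7, where w is the window in days and r the readmission fraction. Rate and cohort size cancel, so the same f applies to the PTH comparison. With none in romosozumab, the observed HR for a true HR of 1.0 is 1/(1+f).

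| w (days) | r | Patients in window | False events | f | Observed HR |
|---|---|---|---|---|---|
| 30 | 5% | 20–49 | 1.0–2.5 | 0.006 | 0.99 |
| 30 | 20% | 20–49 | 3.9–9.9 | 0.023 | 0.98 |
| 90 | 5% | 59–148 | 3.0–7.4 | 0.018 | 0.98 |
| 90 | 20% | 59–148 | 11.8–29.6 | 0.070 | 0.93 |

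Using 0.6 or 0.8 years in the last row gives f = 0.082 or 0.062, and an HR of 0.92 or 0.94. All values are crude, before weighting.

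**5. Equal contamination.** The observed HR is (HR + f)/(1 + f). A true HR of 1.0 stays at 1.0. A true HR of 1.3 (Section 6.3 cites 2.5% versus 1.9%, a ratio of 1.32) reads 1.3705/1.0705 = 1.28 at f = 0.0705, and 1.30 at f = 0.006.

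**The case against.** - **Redaction.** A reader might infer that same-episode readmissions and transfers certainly count as new events. The documents do not support that. Table 2 is blacked out and the design figure is not shown, so a continuation rule may exist. This objection stands. It does not reach the filter, which is stated in plain text, and the visible baseline and follow-up rules still place day 0 in follow-up.
- **Day 0 is narrow.** If the drug is started later in the stay for the event, the admission precedes index and is history. Section 8.3.2 puts in-hospital use of the study drugs below 10%. What remains is admission and first prescription on the same date. This stands as a limit on size.
- **Other covariates.** Table 3 also has cardiovascular hospital days, hospitalizations, coronary and cerebrovascular disease, transient ischemic attack and antiplatelet drugs. Losing one recent-event item leaves proxies. Prevalence in regional core hospitals with emergency departments (Section 8.9.2) may also exceed the planning rate. Both points are fair, but none of these proxies records how recent the event was, and an uncertain prevalence is a reason to exempt the covariate.
- **Channelling.** A reader might infer that the false events fall mainly in the comparators. The label precaution makes this plausible, but the protocol gives no recent-event counts by cohort and does not name recent MI or stroke as the unmeasured contraindication.
- **SAP detail.** Transfer and gap rules are often left to an SAP. Eligibility, the baseline window, the start of follow-up and the filter are fixed in this protocol. Admitting patients with prior events and adjusting for them is a legitimate design, so restriction belongs in a sensitivity analysis.

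**Conclusion.** The point holds in limited form. Under the written rules an index-day MI or stroke admission is an on-drug event, and the recent MI or stroke covariates may be removed from the propensity model. Whether same-episode readmissions are counted cannot be settled from the visible text.

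The size of the bias is unknown. On the assumptions above, the readmission component moves a true hazard ratio of 1.0 to about 0.93 to 0.99 before weighting. That is small beside the Table 4 alendronate intervals, which run from (0.50, 1.91) to (0.70, 1.45). The index-day component has no figure at all.

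A reader might apply the 5% to 20% readmission fraction to everyone with an event in the prior year. That gives 12 to 120 false events against 168 or 420 true ones, and a hazard ratio of 0.78 to 0.93. The documents do not support this range. The fraction has no source in them, and a same-episode readmission after index requires an event shortly before index, not up to a year earlier. If drug starts cluster soon after events, the effect would exceed the even-timing figures, but the protocol gives no data on that.

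The change is worth making because romosozumab events will be few (9.2 to 30.8 expected) and it costs almost nothing.

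**What to change.** 1. In Sections 8.2.4 and 8.2.5, start time at risk the day after index, and classify qualifying admissions on or before the index date as baseline history.
2. In Section 8.3.3, exempt the prior MI and stroke covariates from the 0.5% filter.
3. Add a sensitivity analysis of both primary comparisons restricted to patients with no MI or stroke admission in the 365 days before index, and report recent-event counts by cohort.
4. Confirm that the outcome algorithm does not count transfers or same-episode readmissions as new events, or add a rule to that effect.

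**Cost.** Protocol or SAP wording and one extra analysis on data already planned. A few genuine index-day or early recurrent events will not be counted. The restricted analysis is slightly smaller: about 0.4% to 1.0% of patients at the planning rate, more if recent events are commoner in these hospitals.
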